# 5.2. Summary of Nonclinical and Clinical Studies

#### **5.2.1.** Nonclinical Studies

PTG-300 is a peptidic agent structurally related to natural hepcidin and PTG-300's effects in toxicology studies mimic the effects of hepcidin. In studies of wild type mice, rats and cynomolgus monkeys, single dose subcutaneous or intravenous administration of PTG-300 caused transient decreases in serum iron. The effect on serum iron is brisk in onset (within a few hours of subcutaneous dosing in the thalassemic mouse model) and, depending on the dose, can be quite profound and prolonged. For example, in wild type healthy mice, the effect of a 2.5 mg/kg subcutaneous dose on serum iron persists for at least 30 hours with serum iron declining to a nadir (90% reduction) 10 hours after dosing.

PTG-300 was evaluated in a comprehensive toxicology program including Good Laboratory Practice (GLP)-compliant studies. Specific GLP studies included up to 26-week rat and up to 39-week cynomolgus monkey toxicology studies with 4-week or 5-week reversal periods, as well as genetic toxicology studies to assess potential in vitro mutagenesis, in vitro chromosomal aberrations, and in vivo chromosomal aberrations. Safety pharmacology studies included hERG assay and in vivo studies to assess potential effects on cardiovascular, respiratory, and neurobehavioral parameters.

In toxicology studies, PTG-300 causes exaggerated pharmacological responses in rats and cynomolgus monkeys when dosed for up to 26 or 39 weekly doses. The primary effects of PTG-300 in rats and cynomolgus monkeys are decreases in red blood cell count, hematocrit, and hemoglobin (Hgb) with either compensatory increases of reticulocyte counts at lower doses of PTG-300 or decreases of reticulocyte counts at high doses of PTG-300. Rats dosed with 25 mg/kg PTG-300 for 4 weeks had decreases in red cell mass that were adverse based on magnitude of effect, as well as hepatocellular necrosis that could be secondary to excess iron in liver. Rats dosed with 10 mg/kg/dose for 13 weeks had non-adverse effects consistent with the expected pharmacology of PTG-300. The no-observed-adverse-effect level (NOAEL) was determined to be 10 mg/kg/dose based on a 26-week toxicology study in rats receiving weekly doses of PTG-300 of up to 10 mg/kg/dose. Cynomolgus monkeys dosed with 10 mg/kg PTG-300 for 4 weeks had decreases in red cell mass that were adverse based on magnitude of effect. Cynomolgus monkeys dosed with 6 mg/kg/dose for 13 weeks had no-adverse effects consistent with the expected pharmacology of PTG-300. The NOAEL was determined to be 2 mg/kg/dose following 39 weekly doses of PTG-300 at 0.6, 2, and 6 mg/kg/dose in cynomolgus monkeys. PTG-300 does not cause adverse injection site reactions in rats dosed up to 26 weeks or cynomolgus monkeys dosed up to 39 weeks. In a stand-alone single-dose rat local tolerance study with PTG-300 up to 280 mg/kg (280 mg/mL in dose concentration), the incidence and severity of injection site reactions were generally proportional to the dose and showed incomplete but progressive ongoing reversal by Study Day 14 post-injection. PTG-300 is not mutagenic, and had no apparent effect on cardiovascular, respiratory, or neurobehavioral parameters. All PTG-300-related effects in the GLP toxicology studies were reversed or reversing after a 4- or 5-week treatment-free period. All of the PTG-300-related effects can be monitored clinically.

PTG-300 was also evaluated for embryo-fetal development toxicity in rats and rabbits and fertility and early embryonic development toxicity in both male and female rats. The maternal NOAEL was 3 mg/kg/dose and the NOAEL for the embryo-fetal development was 0.3 mg/kg/dose in the definitive embryo-fetal development toxicity study in rats. The maternal NOAEL was 1 mg/kg/dose and the NOAEL for the embryo-fetal development was 0.3 mg/kg/dose in the definitive embryo-fetal development toxicity study in rabbits. The NOAEL for paternal toxicity and the NOEL for effects on male fertility and early embryonic development were considered to be 10 mg/kg/dose in fertility and early embryonic development toxicity study in male rats. The NOAEL for maternal toxicity and the NOEL for effects on female fertility and early embryonic development toxicity study in female rats.

Principle findings in nonclinical toxicology studies are alterations in red cell mass. PTG-300 has no apparent effect on cardiovascular, respiratory, or neurobehavior in safety pharmacology studies. PTG-300 is not genotoxic.

#### **5.2.2.** Clinical Studies

To date, PTG-300 has been studied in one completed Phase 1 study in healthy subjects. A Phase 2 study of PTG-300 and the study's open-label extension for treatment of  $\beta$ -thalassemia investigated doses over a range of 3 to 80 mg weekly.

Sixty-three patients have been treated in these Phase 2 studies in  $\beta$ -thalassemia. Combining data for the two studies, subjects have been dosed with PTG-300 for durations ranging from 4 weeks to more than 8 months. More than half of the subjects have been dosed for greater than 16 weeks and more than 750 doses of PTG-300 have been administered. Safety data indicate that PTG-300 is well tolerated with no safety concerns.

The frequency of adverse events did not increase with increasing dose of PTG-300. Most adverse events were typical of those expected for subjects with β-thalassemia. The frequency of adverse events did not increase with increasing dose of PTG-300. Adverse events reported in >5% of subjects were upper respiratory tract infection (11.1%), injection site erythema (9.5%), injection site pain (12.7%), urinary tract infections (7.9%), headache (7.9%), fatigue (6.3%), and pyrexia (6.3%). One subject experienced an SAE of confusion, which was considered by the investigator to be possibly related to PTG-300. The event fully resolved within 2 days. In addition, a Phase 2 study of PTG-300 in patients with polycythemia vera requiring phlebotomy has been initiated.

The completed Phase 1 study was a randomized, double blind, placebo controlled, first-in-human (FIH), single ascending dose (SAD) and repeat dose study of PTG-300 administered subcutaneously (SC) in 62 healthy male subjects to evaluate safety/tolerability, PK and PD activity (as assessed by the effect on serum iron parameters). Subjects received single doses of 1 mg to 80 mg PTG-300 or two 40 mg doses 1 week apart.

Following single dose administration of PTG-300 there was a dose-related reduction in serum iron with a maximal reduction of approximately 65% from baseline. The relationship between dose and effect appeared to plateau at 20 mg with higher doses resulting in a longer duration of effect. This effect was sustained for at least 72 hours at higher doses. In subjects that received two 40-mg doses 1 week apart (QW×2) the effects on iron were comparable for both 40-mg

doses. Serum iron levels did not return to baseline prior to the second dose. Serum iron levels generally returned to baseline approximately 1 to 2 weeks following the second dose of PTG-300. Following single dose administration area under the concentration-time curve (AUC) and maximum concentration (Cmax) increased with dose; however, the increase was less than dose-proportional.

PTG-300 was well tolerated by subjects in this study, with no SAEs or dose-limiting toxicities (DLTs) at single doses as high as 80 mg and a repeat dose of 40 mg weekly for 2 weeks. The most frequent adverse events (AEs) were injection site reactions (characterized primarily by a transient erythema at the injection site), headaches and upper respiratory tract infections.

These preclinical and clinical data support clinical development of PTG-300 for the treatment of subjects with HH.

# 5.3. Study Design and Target Population

This is a multicenter, single-arm, open-label study to assess the safety and efficacy of PTG-300 treatment in subjects with HH. Subjects will receive subcutaneous PTG-300 for up to 24 weeks. PTG-300 doses of 10 mg, 20 mg, 40 mg, and 80 mg subcutaneously per week may be tested. In addition, subcutaneous dosing schedules of 10 mg, 20 mg, and 40 mg twice weekly may be tested to achieve a sustained pharmacodynamic effect.

A subset of approximately 6 subjects will participate in a two-way crossover iron absorption substudy.

The study population is subjects with HH who are in maintenance phase and who are on a stable phlebotomy regimen.

## 5.4. Selection of Doses

Subjects will initially receive a subcutaneous dose of 10 mg per week. The dose was based on data in healthy subjects indicating that a dose of 10 mg PTG-300 results in an average reduction of approximately 19% in serum iron. Iron levels returned to baseline within 1 week.

In the current study a subject's dose may be increased to 20 mg per week and subsequently to 40 mg and 80 mg per week based on insufficient decrease in TSAT and acceptable safety. The PTG-300 doses will be administered as subcutaneous doses once a week or as divided doses twice weekly at least 3 days apart (e.g., on Day 1 and Day 4 or 5 of each week). The intent of dose and schedule adjustment is to reduce TSAT and serum iron levels. These higher doses are based on Phase 1 data that showed greater decreases in serum iron and TSAT and longer duration of decrease compared to the 10 mg dose. A Safety Monitoring Committee (SMC) has determined that doses as high as 80 mg per week administered for 8 weeks or more are safe for treating subjects with β-thalassemia.

# 5.5. Summary of Potential Risks and Benefits

Based on the experience of PTG-300 dosing in nonclinical studies and a Phase 1 trial in healthy volunteers, the activities of PTG-300 are related to the proposed mechanism of action, allowing clinical monitoring. Immunologic responses to PTG-300 have not been observed in nonclinical species, however administration of PTG-300 carries theoretical liabilities (immunologically

based responses) associated with the systemic administration of a peptide. In the Phase 1 study PTG-300 was well tolerated, with the majority of AEs other than injection site reactions (primarily transient erythema) considered to be unrelated to PTG-300. In two ongoing Phase 2 studies in β-thalassemia patients, PTG-300 has been well tolerated with no safety concerns, and no deaths have been reported by subjects as of a cutoff date of September 1, 2020.

The potential risk in this study is causing anemia in subjects, assuming no iron is available for erythropoiesis.

The nonclinical and clinical data to date suggests that PTG-300 has a good safety profile and that PTG-300 may be effective for decreasing phlebotomy requirements and decreasing symptoms of iron overload. Thus, the potential benefits appear to outweigh the potential risks of PTG-300 and clinical testing of PTG-300 for HH is appropriate.

A subset of approximately 6 subjects will participate in an iron absorption substudy with the stable isotope Fe. Subjects will receive an oral administration of approximately 4 mg Fe as a ferrous sulfate solution. Stable isotopes are non-radioactive atoms of the same chemical element, which differ only in their number of neutrons (Bodamer 2001). Such studies are common in nutrition science and are often conducted to examine the absorption of selected elements (e.g., iron) from various foods and the impact of various diseases. These tracers are considered safe and may be particularly important for the validation of new treatment modalities, such as novel drug treatments (Bodamer 2001).

# 6. **OBJECTIVES**

The study objectives are as follows:

- 1. To assess the safety and tolerability of PTG-300 in HH subjects.
- 2. To assess the effect of PTG-300 therapy on transferrin saturation (TSAT) and serum ferritin.
- 3. To assess the effect of PTG-300 on iron absorption in a subset of subjects. (For subjects participating in the iron absorption substudy).
- 4. To assess PTG-300's efficacy for treating HH subjects as defined by incidence of phlebotomy.
- 5. To assess the effect of PTG-300 on quality of life (QoL).
- 6. To assess the pharmacokinetics (PK), pharmacodynamics (PD), and immunogenicity of PTG-300.

## 7. INVESTIGATIONAL PLAN

# 7.1. Overall Study Design

This is a multicenter, single-arm, open-label study in subjects with HH. Subjects will receive subcutaneous PTG-300 for up to 24 weeks. Subjects will start at an initial dose of 10 mg per week subcutaneously. The dose may be increased to 20 mg per week, and subsequently to 40 mg and to 80 mg per week if needed, based on tolerability and the pharmacodynamic marker TSAT. In addition, subcutaneous dosing schedules of 10 mg, 20 mg, and 40 mg twice weekly (Day 1 and either Day 4 or Day 5) may be tested.

Based on a review of the TSAT and safety data from at least the first 4 subjects, the starting dose and/or the dosing regimen may be modified for subsequent subjects to reduce exposure to ineffective doses.

Subjects' safety and blood iron parameters (serum iron, serum ferritin, transferrin, and TSAT) will be collected to monitor the pharmacodynamic effect of PTG-300. Effect on phlebotomy need and quality of life (QoL) data (36-Item Short Form Health Survey [SF-36], and Patient's Global Impression of Change [PGI-C]) will also be collected and tabulated.

A subset of subjects (approximately 6 subjects) will participate in a sequential two-way crossover iron (Fe) absorption substudy. The oral iron absorption substudy will be conducted once during the 3-week screening period and then following approximately 4 to 6 weeks of PTG-300 treatment.

Subjects will participate in this study for up to 31 weeks as follows:

- Screening: Up to 3 weeks
- PTG-300 Treatment: Up to 24 weeks (may include iron absorption substudy for selected subjects)
- Safety follow up: 4 weeks.

# **7.1.1.** Screening (Study Day -21 to -1)

After giving written informed consent, subjects will be screened for eligibility according to inclusion/exclusion criteria (see Section 8) within 21 days of dosing. Subjects will continue their individual iron restricted diet throughout the study. During this period liver iron concentration (LIC) will be assessed by magnetic resonance imaging (MRI). Subjects will begin treatment with PTG-300 within approximately 7 days following a regular phlebotomy, with iron parameters measured before (Screening labs) and after the phlebotomy (pre-dose Study Day 1). Each individual subject's pre-phlebotomy serum ferritin level and TSAT will be used as a criterion for phlebotomy during the study, i.e., the threshold at which a phlebotomy should be considered during the study. The serum ferritin level and TSAT obtained during Screening will be used as baseline to assess the change from these measurements post-dosing with PTG-300. All concomitant medications received by the subject beginning 30 days prior to Screening should be collected.

After eligibility has been confirmed, subjects will be enrolled in the study. Those subjects who choose to participate and complete informed consent for the iron absorption substudy will complete their Iron Absorption A session during Screening (See Section 7.1.3 below).

# 7.1.2. Treatment Period (Week 1 to Week 25)

Study Drug Administration: Dosing with PTG-300 at 10 mg will be initiated in the clinic. On clinic visit days, PTG-300 doses will be administered in the clinic. All doses should be administered in the clinic until the subject or caregiver demonstrates the ability to perform subcutaneous injections properly.

Subjects will begin treatment with 10 mg PTG-300 administered weekly. Subjects will receive their first subcutaneous (SC) injection at the clinic and will be instructed on how to self-administer the injection (or have a caregiver administer the injection) and on appropriate safety monitoring before being discharged.

On Study Day 2, subjects will return to the clinic for serum iron parameters and PTG-300 blood concentration (PK) measurements.

Individual Subject Dose and Schedule Escalation: Individual subject dose and schedule will be determined based on the pharmacodynamic (PD) marker TSAT measured at two time points: once at peak PD effect one day post dose and once at trough PD effect. The intent of dose and schedule adjustment is to reduce TSAT and serum iron levels. The dose of PTG-300 may be increased weekly in a sequential manner from 10 mg to 20 mg and, if necessary, to 40 mg and 80 mg until the TSAT is less than approximately 40% at peak PD effect one day post dose and at the trough PD effect prior to the next dose of PTG-300. In addition, the dose may be adjusted to maintain serum ferritin to no more than 1.5 times the screening value or 150 ng/mL, whichever is greater. Investigators may consider once a week or twice a week dosing of PTG-300 to achieve these objectives. The trough PD effect is the TSAT value measured 7 days after the PTG-300 dose (and before the next dose) for once weekly dosing or 7 days after the first dose in a week for twice weekly dosing. For the twice weekly regimen, the doses should be given at least 3 days apart (e.g., on Day 1 and Day 4 or 5 of each week). The twice weekly PTG-300 dose may be escalated to a maximum of 40 mg twice weekly. To facilitate dose escalation and the identification of a therapeutic dose, investigators may assess TSAT values on days subjects come to the clinic for any dose adjustments. These assessments may occur at times other than the regular scheduled visits indicated on the schedule of events.

Subjects will continue treatment by self-administering PTG-300 at home (or in the clinical center as appropriate) for up to 24 weeks based on acceptable safety and tolerability of the drug (Section 7.2). Subjects will return for clinic visits to have safety assessments; serum iron parameters plus soluble transferrin receptor (sTfR), hepcidin and antidrug antibodies (ADA); and efficacy evaluated according to the schedule of assessments.

Subjects' iron parameters will be monitored throughout the study.

Change in Starting Dose: The starting dose may be increased from 10 mg to 20 mg, 40 mg, or 80 mg as appropriate if <2 of the first 4 subjects (or ≤25% of a larger number of subjects) treated at a given dose have both peak and trough TSAT values approximately <40% and no safety signals have been noted.

Criteria for a Phlebotomy: Subjects should undergo an on-study phlebotomy when the subject's serum ferritin levels and TSAT value are higher than the pre-phlebotomy serum ferritin and TSAT values obtained during Screening. In addition, a phlebotomy may be performed when the Investigator assesses it is necessary for subject care.

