# 7.5. Dose Adjustment Criteria

The investigator may increase a subject's dose up to 80 mg per week based on lack of pharmacodynamic (TSAT) response and acceptable safety. The starting dose and/or the dosing regimen will be evaluated and modified to enhance clinical benefit (see Section 7.1.2).

Based on pre-defined safety criteria (see Section 7.2.1), a subject's dosing frequency and dose may be reduced.

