# NOTE: Subjects may require additional visits one day post dose to assess PD effect for dose escalation.

- a Subjects may be rescreened if necessary. Rescreening is considered conducting screening tests outside of the 21-day screening window.
- b Clinical visits should be conducted within an approximately 2-day window (±2 days). All study procedures should occur before study drug administration except as indicated (i.e., PK/PD).

- c Follow-Up procedures are to occur approximately 4 weeks after last dose whether the subject completes the study or terminates early.
- d Subjects enrolled at sites in the United States (US) must sign HIPAA authorization prior to the conduct of any study-specific procedures.
- e Must be conducted within approximately 7 days of PTG-300 dosing. Screening serum iron parameters must be collected before phlebotomy. Note: the prephlebotomy serum ferritin level and TSAT will be used as the subject's individual phlebotomy threshold for the study, i.e., the designated level at which a phlebotomy will be considered.
- f If a subject meets pre-specified criteria for phlebotomy during a visit, schedule a phlebotomy as soon thereafter as possible.
- g Additional tests or examinations, including physical exams, may be conducted as necessary.
- h For women of childbearing potential only.
- i Iron Absorption A is conducted prior to starting PTG-300 (i.e., after the phlebotomy performed during the Screening period). Iron Absorption B should be conducted after approximately 4 to 6 weeks of PTG-300 treatment (one day after PTG-300 administration between Week 4 and Week 6). See Table 3 for the Iron Absorption substudy schedule of events.
- j Study drug administration: PTG-300 is administered weekly or twice weekly. See Section 7.1.2 for details for monitoring TSAT and dose escalation.
- k See Appendix 1 for list of clinical laboratory tests. At Visits 3, 5, and 7, tests will include chemistry and CBC panel only (no urinalysis).
-  These tests should be conducted every 4 weeks at each clinic visit as well as each time point that PTG-300 PK blood samples are collected. In addition, iron parameters must also be measured whenever a subject's dose is escalated (See Section 13.1 and Appendix 2). Additional tests may be obtained as outlined in *Individual Subject Dose and Schedule Escalation* in Section 7.1.2.

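### Table 2 schedules no post-dose blood count or chemistry before Day 29 although 7.1.2 allows weekly dose increases; adding both to the existing Day 15 draw is a cheap improvement

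*Combined protocol and SAP*

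**What the plan says.** **Individual escalation.** Section 7.1.2 states: "The dose of PTG-300 may be increased weekly in a sequential manner from 10 mg to 20 mg". If needed, two further steps follow, the last being 80 mg. Increases run "until the TSAT is less than approximately 40% at peak PD effect one day post dose and at the trough PD effect". On once-weekly dosing the trough is the value 7 days after a dose, taken before the next one. Twice-weekly dosing, up to 40 mg per injection, is also allowed. Section 7.5 permits increases "based on lack of pharmacodynamic (TSAT) response and acceptable safety".

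**Starting dose.** For later subjects Section 7.1.2 adds: "The starting dose may be increased from 10 mg to 20 mg, 40 mg, or 80 mg as appropriate". The conditions are that fewer than 2 of the first 4 subjects at a dose (or no more than 25% of a larger group) have both TSAT values below about 40%, and that no safety signal has appeared. Section 7.1 ties the change to a review of TSAT and safety data from at least the first 4 subjects.

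**Laboratory schedule.** In Table 2 the CBC and clinical laboratory rows are ticked at Screening, Day 1, Visit 3 (Day 29) and every later visit. Both rows are blank at Day 2 and at Visit 2 (Day 15), although iron parameters and PK are drawn on both days. Footnote b reads "All study procedures should occur before study drug administration except as indicated", the exception being PK/PD samples, so the Day 1 safety laboratory tests are pre-dose. Around an escalation, footnotes l and m and Section 13.1.1 call for iron parameters and PK only.

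**Rules that use these laboratory values.** Section 7.2.1 requires a dose reduction for a treatment-related hemoglobin fall of more than 20% from baseline or Grade 2 anemia (whichever is lesser), confirmed by repeat and not caused by phlebotomy. It requires a hold for a treatment-related AST or ALT rise above 3 × ULN.

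**The concern.** The dose can move faster than the laboratory tests meant to check it. The protocol itself names the hazards. Section 5.5 gives anemia as the potential risk if erythropoiesis is deprived of iron. Section 5.2.1 reports adverse red cell mass decreases in rats and monkeys after 4 weeks of dosing, with hepatocellular necrosis in the rats, and says the drug's effects can be followed clinically. Yet the weeks in which the dose may rise fastest have no scheduled hemoglobin or transaminase value after the first dose. An asymptomatic change would not appear in the Day 2 or Day 15 adverse event review, and Section 14.2.4 accepts that an important laboratory abnormality can occur without symptoms. At stake is a delay of up to four weeks in applying Section 7.2.1, unless the investigator chooses to test sooner.

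**Working it through.** The plan gives no figure of its own on this point. The check is a reading of Table 2 and a day count.

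**Inputs.** CBC and chemistry days and the ±2-day visit window: Table 2 and footnote b. Dose steps of 10, 20, 40 and 80 mg, and the raised starting dose: Section 7.1.2. Blood volumes of about 160 mL and 200 mL: Section 13.2. Assumed, because the protocol does not say: the TSAT turnaround time (same day, or up to a week) and 4-9 mL of blood for CBC plus chemistry.

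**Doses before the first scheduled post-dose result.** Weekly dose *i* falls on Day 1 + 7(*i* − 1), that is Days 1, 8, 15 and 22. Visit 3 samples are drawn before the Day 29 dose, so four doses precede them. With same-day TSAT, increases fall on Days 8, 15 and 22. If TSAT takes a week, the Day 8 trough supports an increase on Day 15, the Day 22 trough one on Day 29, and the Day 36 trough one on Day 43.

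| Once-weekly path | Doses on Days 1, 8, 15, 22 (mg) | Total before Day 29 | Increases before Day 29 | Total before a Day 15 pre-dose draw |
|---|---|---|---|---|
| 10 mg start, TSAT same day | 10, 20, 40, 80 | 150 mg | 3 of 3 | 10 + 20 = 30 mg |
| 10 mg start, TSAT after a week | 10, 10, 20, 20 | 60 mg | 1 of 3 | 10 + 10 = 20 mg |
| 80 mg start (later subjects) | 80, 80, 80, 80 | 320 mg | none needed | 2 × 80 = 160 mg |

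Twice-weekly dosing would raise the two escalation totals. It is not computed because the protocol does not fix when a subject would switch.

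**What a Visit 2 draw changes.** The first scheduled result moves from Day 29 to Day 15, 29 − 15 = 14 days earlier (window Day 13-17). There are 22 − 15 = 7 days to read it before the Day 22 dose, or 22 − 17 = 5 if the visit falls at the end of its window. On the fastest path the sample reflects only the 10 mg and 20 mg doses. The first scheduled result after 40 mg or 80 mg is still Day 29, by which time one 80 mg dose has been given. With an 80 mg start, the first check follows two doses instead of four.

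**Blood.** 4/160 = 2.5% to 9/160 = 5.6% of the usual total; 4/200 = 2.0% to 9/200 = 4.5% for a subject escalated to 80 mg.

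**The case against.** The strongest reply is that the gap is a reasonable choice with several safeguards around it.

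- **The TSAT rule limits escalation.** Section 5.5 links anemia to lack of available iron, and subjects who reach 80 mg by Day 22 are those whose iron is not yet suppressed enough. This stands for anemia. It says nothing about AST or ALT.
- **A raised starting dose follows a cohort review.** This stands as a safeguard. However, neither Section 7.1 nor 7.1.2 names a laboratory value for that review or requires Day 29 results before it.
- **Investigators can act sooner.** Section 7.2 and footnote g allow local or additional tests, Section 15.3 allows clinical laboratory values to guide decisions, and Section 7.2.1 also covers an investigator-determined hemoglobin decrease. So a reader might infer that the safety rules cannot operate before Day 29, or that escalation goes unmonitored. The documents do not support that: adverse events are reviewed on Days 2 and 15, and vital signs and ECG are taken on Day 2. What is missing is a required hemoglobin or transaminase value.
- **Prior data are reassuring.** Phase 1 saw no serious events or dose-limiting toxicity at single doses up to 80 mg. Adverse event frequency did not rise with dose in 63 β-thalassemia patients, and a safety committee judged 80 mg weekly for at least 8 weeks (8 × 80 = 640 mg, twice the 320 mg above) safe in that disease. The rat necrosis came at 25 mg/kg, against 80/90 = 0.9 to 80/60 = 1.3 mg/kg, unscaled, at an assumed 60-90 kg. This stands, although Section 5.2.2 reports no exposure in hemochromatosis.
- **A Day 15 hemoglobin is hard to attribute.** It comes 14 to 21 days after the screening phlebotomy, and the rule excludes falls due to phlebotomy and needs a repeat. This stands. The value must be read against the post-phlebotomy Day 1 CBC, and a low one prompts a repeat rather than an automatic reduction.

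**Conclusion.** The concern holds as a cheap improvement and no more. The calendar gap is certain: no scheduled post-dose CBC or chemistry exists before Day 29 (Day 27 at the earliest), and four once-weekly doses can precede it.

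The exposure inside the gap is conditional. Reaching 80 mg on Day 22 needs same-day TSAT results, which the protocol does not promise; with a one-week turnaround only one increase precedes Day 29. The 150 mg total is specific to once-weekly dosing and is not an upper limit. The 320 mg total applies only to later subjects, after the cohort review and with no safety signal.

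A reader might also infer that subjects are exposed to a demonstrated early harm. The documents do not support that either: nothing in them shows a hemoglobin or ALT effect by Day 22 at these doses. The case rests on the low cost of the change and on hazards the protocol itself lists. The gain is greatest with a raised starting dose and modest on the fastest escalation path.

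**What to change.** In Table 2, tick CBC and clinical laboratory tests at Visit 2 (Day 15), drawn with the iron and PK sample already taken there. Footnote k now says "At Visits 3, 5, and 7, tests will include chemistry and CBC panel only (no urinalysis"; add Visit 2 to that list of visits. State that the result is checked against Section 7.2.1 before the Day 22 dose and that hemoglobin is compared with the Day 1 post-phlebotomy value. Update the blood volume in Section 13.2.

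The cost is one protocol amendment, with the ethics re-approval that Section 16.5.1 requires, a small laboratory charge, and an assumed 4-9 mL of blood per subject. No visit or needle stick is added. Escalation is not slowed if the result is back before the Day 22 dose, although a low hemoglobin will need a repeat that the schedule does not provide.
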